## **11.1 Primary Efficacy Measure:**

• Insomnia Severity Index (ISI)

The ISI is a 7-question survey assessing symptoms of insomnia over the past week. Maximum score is 28, with higher scores indicating greater severity. The ISI has been validated for use in insomnia research (Bastien, Vallieres, Morin 2001).

### **11.2 Secondary Efficacy Measures:**

#### • sQUAL (Subjective Quality of Sleep)

This is a single question, "How would you describe the quality of your sleep last night?" There are 4 choices to answer: Choices: 1 = poor, 2 = fair, 3 = good, 4 = excellent

#### • sFRESH (Subjective refreshed feeling on waking)

This is a single question, "How refreshed do you feel this morning?" There are 5 choices to answer:

Choices: 1= not at all refreshed, 2 = a little refreshed, 3= moderately refreshed, 4= quite a bit refreshed, 5= extremely refreshed

#### • Change in Modified Fatigue Index Scale (MFIS) Score at 2 weeks vs baseline.

The MFIS is a well-validated fatigue measure in MS (Tellez et al. 2005). The MFIS has a Cronbach's alpha of 0.81 (National MS Society). In MS, it has been found to have intratest reliability, no ceiling or floor effects and greater sensitivity to change than the FSS (Kos et al. 2003). The test has 21 items with physical, cognitive and psychosocial subscales. Subjects will complete the MFIS as the first test conducted on the day of visit. Their ratings on the 21-item questionnaire will be based on their fatigue experience over the previous 1 week. The total MFIS score will be used for primary efficacy measure.

#### • Fatigue Visual Analogue Scale (VAS-F)

The VAS-F is a 10-cm line that asks subjects to rate fatigue on a scale of 0 (no fatigue) to 100 (fatigue "as bad as it can be") by marking their fatigue level on the line (See appendix). The VAS-F has been validated as a measure of response to therapy in MS fatigue populations (Rammohan et al.2002, Weinshenker et al. 1992). Ratings will be based on their fatigue experience over the previous 1 week.

#### • Wearable Sleep Monitor (WSM)

A Fitbit device will be worn throughout the study. A 7-night average for screening period will be compared with the final 7-night average for both treatment periods. Outcome measures based on the wearable sleep monitor will include:

- Total minutes asleep
- Minutes awake during time in bed
- Number of awakenings
- Time in bed

### • Subjective Global Impression of Change

This is a single question: "How would you rate change in your level of physical and mental function, during the study?" Response ranging from "Extremely improved", "Much improved", "Slightly improved", "No change", "Slightly worse", "Much worse", and "Extremely worse".

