#### SCHEDULE OF EVENTS

Parameter	Screening Clinic Visit 1	Baseline Clinic Visit 2	Phone Visit 1	Phone Visit 2	Phone Visit 3	Phone Visit 4	Phone Visit 5	Unscheduled Visits
	Week # 0	Week # 1-2		Week #3-4	Week #5-6		Week #7-8	
Medical History	Х							
Informed consent	Х							
Physical Examination/ Visit with MD	Х	Ŧ						Х
Vital Signs	Х							
Urine pregnancy test for females *	Х							
Laboratory testing **	Х							
Beck Depression Inventory II	Х			Х			Х	
BDI - Q9			Х			Х		
Current Medication	X	Х	Х	Х	Х	Х	Х	
EDSS	Х							
Randomization		Х						
Drug dispensing		Х						
Fatigue Severity Scale	X							
MFIS		Х		Х			Х	
Insomnia Severity Index		Х		Х			Х	
Fatigue VAS		Х		Х			Х	
Sleep diary		Х		Х			Х	
Wearable sleep monitor review		Х		Х			Х	
Step count		Х		Х			Х	
Global impression		Х		Х			Х	
Adverse Event assessment		Х	Х	Х	Х	Х	Х	Х
Study drug pill counts							Х	

Ŧ Optional, indicated for any safety issues that arise
\* As indicated by fertility status
\*\* Laboratory testing: CBC, CMP

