Physical examination will be performed, both a general medical examination including vital signs and a neurological examination. Neurological exam will include disability rating by expanded disability status scale (EDSS) (Kurtzke 1983). Laboratory testing will include complete blood count (CBC), complete metabolic panel (CMP), with calculation of the Child-Pugh score for any subjects with liver dysfunction. Pre-menopausal women without surgical sterilization will have urine human chorionic gonadotropin (hCG) measured.

The wearable activity/sleep monitor will be dispensed at this visit to all subjects who meet eligibility criteria. This will be a FitBit™ device worn by the subjects throughout the remainder of the study. The research coordinator will oversee patient education around FitBit use. The FitBit is easy for subjects to put on and requires minimal user programming to upload data. Recorded outcomes are described below (see outcome measures). Subjects will be encouraged to wear the monitor 24-hours per day. Patients will be instructed to complete a sleep diary for seven days prior to next visit (see 11. Outcome measures).

## 10.3 Baseline Clinic Visit 2

Clinic Visit 2 will occur within 7-14 days after the screening visit. In addition to screening for eligibility, medications will be reviewed again to ensure stability of the MS medication regimen and absence of any prohibited medications.

Following confirmation of eligibility, an eligible patient will complete the baseline assessments of the insomnia severity index (ISI), modified fatigue impact scale (MFIS), Fatigue visual analogue scale (VAS-F), Global impression. The following measures will be provided for the participants to take home for use at the time of Phone Visit 2 and Phone Visit 5: Study scales (ISI, MFIS, VAS-F, BDI, Global impression). Sleep diaries will be provided for use after Phone Visit 1 and Phone Visit 3.

Following confirmation of eligibility, an eligible patient will be randomized in a 1:1 randomization scheme to receive suvorexant 10 mg qhs or placebo. Randomization will occur at the research pharmacy of EvergreenHealth using a computer-generated randomization list. The pharmacist will maintain a codebook indicating the treatment allocation of each subject. Study medication will be delivered by the research pharmacist to the research study staff from the

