research pharmacy (a separate locked room containing only research medications). The investigating physicians and research coordinator will be blinded as to treatment arm until the code is broken. The randomization code may be broken by the investigator only in a medical emergency. The reasons for such an emergency will be documented carefully. The subjects will receive 2 pill bottles, each containing identical appearing active or placebo study medication tablets, with identification known only to the research pharmacist. See Section 7.2 regarding study medication preparation and distribution.

The patient will be provided with pre-stamped and pre-addressed envelopes for return of unused study medication and study diaries at end of study.

### 10.4 Phone visit 1

Phone Visit 1 will occur 5-7 days after Clinic Visit 2 to review safety and tolerability through questioning about adverse events. BDI Q9 (suicidality risk) will be administered. Subjects with answer of 2 or 3 will be asked to discontinue study medication immediately and unscheduled visit or emergency referral will be arranged. Subjects with BDI Q9 score 0 or 1 who report no AEs on suvorexant 10 mg po QHS (or matched placebo) and who report a persistent sleep disturbance will be titrated to suvorexant 20 mg po QHS (or matched placebo) using a titration decision algorhythm. At this visit, subject will be reminded to wear sleep monitors and to start recording sleep diaries every morning.

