### 10.5 Cross-over Phone Visit 2 (14 days post treatment)

Phone Visit 2 will occur at the completion of the first treatment period (day 14 following baseline). Medications will be reviewed again to ensure absence of any prohibited medications. Any possible adverse events (AE) will be assessed.

Study scales (ISI, MFIS, VAS-F, BDI, Global impression) will be self-administered by the participant with study staff oversight, as needed. Data from the wearable activity / sleep monitor will be collected. Completion of the 7-days sleep diary and scales (sQUAL and sFRESH) will be verified remotely.

Subjects will be instructed to take no study medication for one week, then to start taking the study medication (active or placebo) for Period 2.

### 10.6 Phone Visit 3 : Start of Treatment Period 2

Phone Visit 3 will occur 1 week after Phone Visit 2 (day 21 after baseline) and will mark the beginning of treatment period 2. Medications will be reviewed again to ensure stability of the MS medication regimen and absence of any prohibited medications. Any possible adverse events (AEs) will be assessed.

Subjects will be instructed to begin taking drug from the bottle marked "Period 2.". All subjects who received active medication in treatment period 1 will take placebo, and all subjects who received placebo in treatment period 1 will take active medication (10mg) while double blind.

## 10.7 Phone Visit 4

Phone Visit 4 will occur 5-7 days after Phone Visit 3 to review safety and tolerability through questioning about adverse events. BDI Q9 (suicidality risk) will be administered. Subjects with answer of 2 or 3 will be asked to discontinue study medication immediately and unscheduled visit or emergency referral will be arranged. Subjects with BDI Q9 score 0 or 1 who report no AEs on suvorexant 10 mg po QHS (or matched placebo) and who report a persistent sleep disturbance will be titrated to suvorexant 20 mg po QHS (or matched placebo) using a titration decision algorhythm. At this visit, subjects will be reminded to wear sleep monitors and to start recording sleep diaries.

### 10.8 Termination Phone Visit 5

Phone Visit 5 (final visit) will occur 2 weeks after Phone Visit 3 (day 35 after baseline). Medications will be reviewed again. Any possible AE will be assessed.

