# 11. Outcome Measures

All outcome measures will be based on end of treatment period compared to baseline visit.

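### The global impression item has no period-specific window, so its day-35 answer can cover both treatments and the washout; 10.3 and 10.7 also disagree on when the Period 2 diary starts

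*Combined protocol and SAP*

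**What the plan says.** **Global impression.** The only wording given (section 11.2) is "How would you rate change in your level of physical and mental function, during the study", answered on a seven-level scale from extreme improvement to extreme worsening. The Schedule of Events marks "Global impression" at Baseline Clinic Visit 2, Phone Visit 2 and Phone Visit 5. Section 10.3 confirms the baseline use, listing "Fatigue visual analogue scale (VAS-F), Global impression" among the assessments completed at that visit. Sections 10.5 and 10.8 confirm the two later uses. Section 7.2 has study drug first dispensed at Visit 2. Section 11 opens with a rule for every endpoint: "All outcome measures will be based on end of treatment period compared to baseline visit".

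The other patient-reported secondary measures have short windows. For the VAS-F, "Ratings will be based on their fatigue experience over the previous 1 week"; the MFIS uses the same week. sQUAL refers to the previous night and sFRESH to the morning of rating. The primary ISI also covers the past week (11.1).

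**Sleep diary.** Section 10.3 states: "Sleep diaries will be provided for use after Phone Visit 1 and Phone Visit 3". For Period 1, section 10.4 agrees: at Phone Visit 1 the "subject will be reminded to wear sleep monitors and to start recording sleep diaries every morning". For Period 2, section 10.7 gives the start-recording reminder at Phone Visit 4, and "Phone Visit 4 will occur 5-7 days after Phone Visit 3". The diary lasts seven days per period (note in 11.3). Section 13 analyses the final week of each treatment period.

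**The concern.** In a crossover, each end-of-period rating has to reflect the treatment of that period. At day 14 the item can cover only Period 1 (plus screening, if the patient counts it). At day 35 it can cover Period 1, the washout and Period 2. The two ratings being contrasted may therefore have different windows, and the later one may contain the other treatment. Patients complete the form themselves at home, with staff oversight only where needed, and nothing in the plan makes them all read it the same way. No analysis can later recover which period a patient had in mind.

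At baseline the item asks about change before any study drug has been taken. Applying section 11 literally then compares one change rating with an earlier change rating, which has no clear meaning.

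The diary is a separate, smaller matter. If the Period 2 diary is started and finished early, the sQUAL and sFRESH entries fall outside the analysed week, and mostly before the Phone Visit 4 titration decision. The Period 1 diary follows its own titration call, so the two periods would not be measured alike.

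**Working it through.** **The plan's own computed figure.** Section 13 gives 81% power for the ISI with 45 analysable subjects (50 × 0.9), a difference of 1.75 and an SD of the difference of 4.1. The normal approximation gives Φ(1.75 × √45 / 4.1 − 1.96) = Φ(2.86 − 1.96) = 0.817; the noncentral t with 44 degrees of freedom gives 0.800. The figure reproduces, and nothing below touches it.

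**Span of the global item at day 35.** From 10.5, 10.6 and 10.8, in days after baseline:

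- Period 1: days 0–14 (14 days)
- Washout: days 14–21 (7 days)
- Period 2: days 21–35 (14 days)

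Period 2 share counted from baseline: 14/35 = 40%. Screening is 7–14 days before baseline (10.3), so counted from screening the share is 14/(35 + 7) = 33% to 14/(35 + 14) = 29%.

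**Direction of any mixing.** Let *a* and *p* be a patient's true ratings on active drug and placebo. Let *w* be the weight the day-35 answer gives to Period 1, leaving the washout aside.

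- Active first: day 14 gives *a* and day 35 gives (1 − *w*)*p* + *wa*. Active minus placebo is (1 − *w*)(*a* − *p*).
- Placebo first: day 14 gives *p* and day 35 gives (1 − *w*)*a* + *wp*. Active minus placebo is again (1 − *w*)(*a* − *p*).

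Mixing shrinks the contrast toward zero in both sequences, so averaging over sequences does not remove it. A patient who answers for now versus study start has *w* = 0 and there is no loss. The documents give no basis for a value of *w*, so the loss cannot be quantified.

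**Diary overlap.** Count mornings, with morning *d* reporting the night before. The final week of Period 2 is mornings 29–35. Each row is a strict seven-morning diary.

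| Start | Mornings recorded | Overlap with final week |
|---|---|---|
| Right after Phone Visit 3 (day 21) | 22–28 | 0 of 7 |
| Phone Visit 4 on day 26 | 27–33 | 5 of 7 |
| Phone Visit 4 on day 27 | 28–34 | 6 of 7 |
| Phone Visit 4 on day 28 | 29–35 | 7 of 7 |

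In Period 1, a start at Phone Visit 1 (day 5, 6 or 7) against mornings 8–14 also gives 5, 6 or 7 of 7. So the Phone Visit 4 start matches Period 1 and the Phone Visit 3 start does not. Of mornings 22–28, only 0–2 come after the possible titration at Phone Visit 4; for a diary begun at that visit all 7 do.

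**The case against.** - **Section 11 may settle the reading.** It defines outcomes as end of period relative to baseline, and for a change item that naturally means now versus study start, where dilution is nil. This is fair as far as it goes, but the rule instructs the analyst. The patient sees only the question.
- **The baseline rating may be harmless.** Within a patient, (Period 2 − baseline) − (Period 1 − baseline) = Period 2 − Period 1, so it cancels. That holds for a within-patient period difference. Section 13 instead describes comparing baseline with each period by treatment arm, and there it does not simply cancel.
- **The harm is conjectural.** The calendar fractions are not weights, any bias is toward zero, and this is one single-question secondary measure in a pilot study. All of that stands, and it limits the weight of the point.
- **The diary sentence in 10.3 concerns supply.** Phone Visit 4 is also after Phone Visit 3, and the 0-of-7 case needs a patient to start on day 21 and stop despite the later reminder to begin recording. It is indeed a worst case, and a patient who records through day 35 loses nothing. The parallel with Phone Visit 1 still points to a wrong visit number. Nor does a Phone Visit 4 start guarantee the full final week: a strict seven-day diary can miss up to two mornings.
- **The anchor is a choice.** Change since the start of the current period would be a different estimand. The pre-treatment anchor is preferred because it agrees with section 11.

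**Conclusion.** Both points hold. The global impression is the only patient-reported secondary measure without a short, period-specific window, and its day-35 answer can span both treatments and the washout. Period 2 makes up 40% of that span from baseline, or 29–33% from screening. The effect on the contrast is a risk of dilution of unknown size, possibly nil, and no loss of power is claimed. The baseline rating carries no treatment information and makes the section 11 comparison meaningless for this item. This takes the baseline form to be the item worded in 11.2, since no separate severity version is defined.

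Sections 10.3 and 10.7 must be reconciled on the Period 2 diary. The worst case is 0 of 7 mornings in the analysed week, against 5–7 of 7, assuming the patient stops after exactly seven days.

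The ISI endpoint and its power are unaffected. The change should be made before data are collected, because the wording cannot be repaired afterwards.

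**What to change.** 1. Reword the item with a pre-treatment anchor and a one-week window, for example: *Thinking of the past week, how does your physical and mental functioning compare with before you first took any study tablets?* Keep the seven response levels.
2. Remove the item from the baseline visit in the Schedule of Events and from the baseline assessments in 10.3.
3. Add to section 11: *Exception: the global impression is not compared with baseline; the Phone Visit 2 and Phone Visit 5 ratings are compared within patient.*
4. In the diary sentence of 10.3, change Phone Visit 3 to Phone Visit 4, to agree with 10.4, 10.7 and the final-week analysis in section 13.

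The cost is one reworded question, one schedule cell with its mention in 10.3, one added sentence and one visit number. There is one form fewer at baseline, and no extra visits or patients.

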#### **11.3 Exploratory Efficacy Measures:**

• Daily step count

Data obtained from wearable activity monitor will be recorded. The average of 7 days will be calculated.

#### • Beck Depression Inventory

#### Note on sleep diary content

During screening and each treatment period, patients will complete a 7-day sleep diary. They will be asked to record each morning the following:

- 1. The time they went to bed
- 2. Approximate time they went to sleep
- 3. Number of awakenings
- 4. Approximate time they awoke for the last time (in the morning)
- 5. Time they got out of bed in the morning
- 6. sFRESH
- 7. sQUAL

### Note on the Use of the Wearable Sleep Monitor and activity monitor

Of note, inability or unwillingness to use the WSM or activity monitor are specifically *not* exclusion criteria. Those subjects who are unable or unwilling to use the WSM or activity monitor correctly will be allowed in the study (provided all eligibility criteria are otherwise met), and the observations from their WSM activity monitor variables will be treated as missing data.

## **12.** Safety Monitoring

### 12.1 Safety measures:

Laboratory testing: All subjects: CBC, CMP. As-indicated: urinary pregnancy testing Safety will be monitored by adverse event (AE) reporting, physical examination, laboratory evaluation.

Monitoring for suicidality: The BDI is being performed due to suvorexant being a central nervous system depressant, which could cause suicidal ideation and behavior. This test is performed at screening, baseline and final visit. At phone visits 2 and 5, the BDI is administered and at phone

visit 1 and 4, question 9 of the BDI is administered to ascertain suicidal thoughts or wishes. A score of 2 or 3 on BDI question 9 indicates that the patient would be at significant suicide risk. A high score on the BDI or BDI question 9 at any point would result in immediate discontinuation of the study medication and unscheduled visit or emergency room referral, as indicated.

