## 8.2 Exclusion criteria

- Use of potential MS-associated fatigue drugs within 3 days of screening until study completion, including modafinil, armodafinil, amantadine, methylphenidate, products with amphetamine or dextroamphetamine.
- Use of any of any prohibited medication (see below) from 3 days prior to screening to termination visit.
- Female who is breast-feeding, pregnant, or has the potential to become pregnant during the course of the study (fertile and unwilling/unable to use effective contraceptive measures).
- History of narcolepsy.

- Has a diagnosis of severe chronic obstructive pulmonary disease (COPD), defined by FEV1 < 50% of predicted on most recent available pulmonary function test (PFT). PFT is not required if the subject has never been diagnosed with COPD.
- Has a history of severe obstructive sleep apnea (OSA), with severe OSA defined as having an apnea-hypopnea index (AHI) > 30 on prior polysomnograph (PSG). PSG is not required if there is no history suggesting severe OSA.
- Is concurrently using other central nervous system(CNS) depressants, including alcohol, except that one alcoholic drink per day will be allowed for those with normal hepatic function provided the drink is consumed at least 2 hours prior to or 8 hours after taking the study drug. Medical marijuana is allowed if consumed at the patient's usual dose at least 2 hours prior to or 8 hours after taking the study drug. Recreational marijuana is not allowed from screening until end of study.
- Has evidence at screening of severe hepatic impairment as defined by a Child-Pugh score > 10.
- Cognitive impairment that in the opinion of the investigator would prevent completion of study procedures or the ability to provide informed consent.
- Suicidality or severe depression as measured by screening Beck Depression Inventory II (BDI) score > 28 or score of >1 on BDI Q9 (suicidality screen) at any time during the study.
- Any other serious and/or unstable medical condition.

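### Section 12.1 places a BDI at baseline, but the Schedule of Events has neither BDI-II nor Q9 at Clinic Visit 2, so a subject can be randomised on a Q9 score 7 to 14 days old

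*Combined protocol and SAP*

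**What the plan says.** Section 12.1, in its paragraph on suicidality monitoring, gives the BDI timing as "This test is performed at screening, baseline and final visit". It then adds the full BDI at Phone Visits 2 and 5 and question 9 alone at Phone Visits 1 and 4.

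In the Schedule of Events, the row "Beck Depression Inventory II" is marked at Screening, Phone Visit 2 and Phone Visit 5, and the Q9 row at Phone Visits 1 and 4. Neither is marked at Baseline Clinic Visit 2. The physician visit in that column carries the footnote "Optional, indicated for any safety issues that arise".

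Section 10.3 says of the subject at Clinic Visit 2: "will complete the baseline assessments of the insomnia severity index (ISI), modified fatigue impact scale (MFIS), Fatigue visual analogue scale (VAS-F), Global impression". Its only mention of the BDI is among the forms taken home for Phone Visits 2 and 5. On timing: "Clinic Visit 2 will occur within 7-14 days after the screening visit". On eligibility: "In addition to screening for eligibility, medications will be reviewed again to ensure stability of the MS medication regimen", and then "Following confirmation of eligibility, an eligible patient will be randomized in a 1:1 randomization scheme".

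Section 8.2 excludes suicidality or severe depression on these limits: "screening Beck Depression Inventory II (BDI) score > 28 or score of >1 on BDI Q9 (suicidality screen) at any time during the study".

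Section 11 defines every outcome measure as end of treatment period against the baseline visit. The BDI is listed in 11.3 as exploratory.

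**The concern.** The current text gives two different answers to whether a BDI is done at Clinic Visit 2. A site working from 12.1 would have a same-day Q9 score. A site working from the Schedule and 10.3 would not. The study is described as multi-center, so both practices could occur.

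The visit matters because the protocol asks for eligibility to be confirmed there before randomisation, and study drug goes home the same day. The two limbs of the 8.2 criterion are worded differently. The BDI total above 28 is a screening value, so the screening form settles it. The Q9 limb is open-ended in time, so it is most naturally read as still applying at Clinic Visit 2. The only re-check that 10.3 spells out is of medications. If Q9 rises to 2 between screening and Clinic Visit 2, a site following the Schedule has no score to show it, and the subject could be randomised and next asked Q9 by phone 5 to 7 days later.

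A smaller consequence concerns analysis. Under the Schedule, the exploratory BDI has no value at the visit that section 11 names as the comparator.

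**Working it through.** No power or sample size figure is involved. The check sets the sources side by side and works through the visit windows.

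**1. Where each source places the BDI or Q9**

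| Contact | Section 12.1 | Schedule of Events | Visit text in section 10 |
|---|---|---|---|
| Screening Clinic Visit 1 | BDI | BDI-II | BDI (10.2) |
| Baseline Clinic Visit 2 | BDI | blank | not among baseline assessments (10.3) |
| Phone Visit 1 | Q9 | Q9 | Q9 (10.4) |
| Phone Visit 2 | BDI | BDI-II | BDI (10.5) |
| Phone Visit 3 | none | blank | none (10.6) |
| Phone Visit 4 | Q9 | Q9 | Q9 (10.7) |
| Phone Visit 5 | BDI | BDI-II | BDI (10.8) |

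The sources agree at every contact except Baseline Clinic Visit 2.

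**2. Is the blank cell an extraction fault?** Counting cells, the BDI-II row has marks in columns 1, 4 and 7, and the Q9 row in columns 3 and 6. The MFIS row has marks in columns 2, 4 and 7, and the MFIS is a baseline measure in 10.3, so column 2 is Baseline Clinic Visit 2. The rows are intact and the blank is real.

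**3. Could baseline in 12.1 mean screening?** No. The same sentence lists both as separate time points.

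**4. Intervals if the Schedule is followed**

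- Screening to Clinic Visit 2 (10.3): 7 to 14 days. This is the age of the latest Q9 at randomisation.
- Clinic Visit 2 to Phone Visit 1 (10.4): 5 to 7 days.
- Screening Q9 to next Q9: 7 + 5 = 12 days at the shortest, 14 + 7 = 21 days at the longest.
- Screening BDI total to next BDI total, with Phone Visit 2 at day 14 after baseline (10.5): 7 + 14 = 21 to 14 + 14 = 28 days.

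If 12.1 is followed, the Q9 score at randomisation is from the same visit. The next one is still 5 to 7 days later.

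**5. Effect on the exploratory BDI.** Write B for the baseline score and S and P for a subject's end-of-period scores on suvorexant and placebo. The treatment contrast is (S − B) − (P − B) = S − P. A shared baseline cancels, so the contrast does not depend on which pre-dose score is used. The reported changes S − B and P − B do depend on it. Under the Schedule the only pre-dose B is the screening score.

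**The case against.** The strongest reply has four parts.

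First, Q9 is well covered elsewhere: at screening within the BDI-II, and at Phone Visits 1, 2, 4 and 5. This stands. A reader might infer that the Q9 exclusion has no instrument behind it. The documents do not support that: 12.1 itself names a baseline BDI, and the shortfall in the Schedule is at one visit.

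Second, Clinic Visit 2 is not without a safety check. The Schedule marks an adverse event assessment there, 12.2 provides for questioning by the investigator and counts symptoms that emerge or worsen after screening, and a physician visit is available if a safety issue arises. This stands too, so it would be wrong to say that a site depends only on what the subject volunteers. But general questioning does not produce the score that 8.2 uses, and at Phone Visits 1 and 4 the protocol asks Q9 in addition to adverse event questions.

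Third, the open-ended wording in 8.2 may be meant to work through the on-study stop rules in 10.4, 10.7 and 12.1, and it does not expressly require a repeat Q9 at Clinic Visit 2. That is a possible reading. It does not explain what a site should use when 10.3 tells it to confirm eligibility again.

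Fourth, the 12.1 sentence may be left over from a plan with more clinic visits, since 7.1 and the table of contents still refer to clinic cross-over and termination visits. The 10.3 list is also not exhaustive: it leaves out the adverse event assessment that the Schedule marks. So 10.3 is weak support, and the conflict is essentially one Schedule cell against one word in 12.1. Deleting that word would remove the contradiction, but eligibility would still be confirmed without a current Q9.

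**Conclusion.** The inconsistency is real and worth correcting. Its size is limited: under the Schedule, the Q9 available at randomisation is 7 to 14 days old and was taken before any study drug, and the exploratory BDI has no baseline-visit value. The eligibility part rests on reading the Q9 limb of 8.2 as applying at Clinic Visit 2, which its wording favours but does not state outright.

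Two stronger readings should be resisted. One is that the gap leaves on-drug suicidality unmonitored. It does not: the first on-drug Q9 is 5 to 7 days after Clinic Visit 2 whether or not a baseline score is taken. The protocol's statement that the drug could cause suicidal ideation concerns risk after dosing, whereas the interval at issue is before it. The other is that the efficacy results are compromised. The ISI is collected at Clinic Visit 2, so the primary analysis and its power are untouched, and the within-subject BDI contrast does not depend on the baseline. The documents give no rate at which Q9 newly reaches 2 or 3 between the two visits, so no number of affected subjects can be stated.

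**What to change.** Mark the BDI-II at Baseline Clinic Visit 2 in the Schedule of Events and add it to the baseline assessments in 10.3. Have it scored before randomisation and dispensing, and state that a subject with Q9 of 2 or 3 is not randomised. This brings both places into line with 12.1, gives the eligibility confirmation a current Q9, and supplies the section 11 baseline value.

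If the sponsor did not intend a full BDI at that visit, ask Q9 alone there, as at Phone Visits 1 and 4. In that case delete baseline from the BDI sentence in 12.1 and name the screening BDI as the section 11 baseline for that measure.

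The cost is a few minutes with an existing form at an existing visit, edits to the Schedule and 10.3 (and, under the alternative, to 12.1 and section 11), and possibly a few subjects found ineligible at Clinic Visit 2.
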